4. INVESTIGATIONAL PLAN

4.1. Overall Study Design and Plan

This is a Phase 1, open label, dose-escalation clinical trial to evaluate the safety, reactogenicity, and immunogenicity of Sm-p80 + GLA-SE candidate schistosomiasis vaccine (SchistoShield®) in healthy adults 18 through 55 years of age. The Sm-p80 antigen is a recombinant protein produced in *E. coli* and GLA-SE is an immunological adjuvant.

Five treatment groups, each including nine subjects, will receive three intramuscular (IM) injections of 0.5 mL of designated study product on either Days 1, 29, and 57 or on Days 1, 29, and 180. Group A (unadjuvanted comparator) will receive 100 µg Sm-p80 alone on Days 1, 29, and 57; Group B (low dose standard schedule) will receive 10 µg Sm-p80 + 5 µg GLA-SE on Days 1, 29, and 57; Group C (mid dose delayed booster) will receive 30 µg Sm-p80 + 5 µg GLA-SE on Days 1, 29, and 180; Group D (mid dose standard schedule) will receive 30 µg Sm-p80 + 5 µg GLA-SE on Days 1, 29, and 57; Group E (high dose standard schedule) will receive 100 µg Sm-p80 + 5 µg GLA-SE on Days 1, 29, and 57. Dose escalation will proceed as described in the Protocol Summary (protocol v2.0).

Reactogenicity will be measured by the occurrence of solicited injection site and systemic reactions from the time of each study product injection through seven days after each study product injection. Unsolicited AEs of all severities, and concomitant medications, will be collected from the time of each study product injection through the next 28 days. During period of follow-up outside of the 28-day post-vaccination interval, only SAEs, medically attended adverse events (MAAEs), new onset chronic medical conditions (NOCMCs), and potentially immune-mediated medical conditions (PIMMCs) will be collected. Clinical laboratory evaluations for safety will be performed on venous blood collected prior to, and approximately seven days after, each study vaccination.

Immunogenicity testing will include measuring titers of total IgG against the Sm-p80 protein by ELISA. Gene expression will be evaluated using RNA Seq analysis from whole blood.

4.2. Discussion of Study Design, Including the Choice of Control Groups

4.3. Selection of Study Population

The study population of 45 subjects will be enrolled from a population of healthy, *Schistosoma*-naïve subjects ages 18 through 55 years at a single study site in Seattle, Washington.

Subject Inclusion and Exclusion Criteria must be assessed by a study clinician licensed to make medical diagnoses and listed on the Form FDA 1572 as the site PI or sub-investigator. No exemptions are granted on Subject Inclusion/Exclusion Criteria in DMID-sponsored studies. Questions about eligibility will be directed toward the DMID Medical Officer.

Subject Inclusion Criteria

Subjects must meet all the following inclusion criteria to be eligible for enrollment in this study

1. Male or non-pregnant female 18 through 55 years of age, inclusive, at the time of consent
2. Able and willing to participate for the duration of the study and able to understand and comply with planned study procedures
3. Able and willing to provide written (not proxy) informed consent

4. Is in good health, as judged by the investigator, and determined by medical history and physical examination*

*Existing medical diagnoses or conditions (except those in the Subject Exclusion Criteria) must be deemed as stable. A stable medical condition is defined as no change in prescription medication, dose, or frequency of medication in the last three months (90 days) and health outcomes of the specific disease are considered to be within acceptable limits in the last six months (180 days). Any change due to change of health care provider, insurance company, or that is done for financial reasons, as long as in the same class of medication, will not be considered a violation of this inclusion criterion. Any change in prescription medication due to **improvement** of a disease outcome, as determined by the site PI or appropriate sub-investigator, will not be considered a violation of this inclusion criterion. Subjects may be on chronic or as needed (prn) medications if, in the opinion of the site PI or appropriate sub-investigator, they pose no additional risk to the subject safety or assessment of solicited events and immunogenicity.

Topical, nasal, and inhaled medications (with the exception of some uses of corticosteroids as outlined in the Subject Exclusion Criteria), vitamins, and contraceptives are permitted.

5. Women of childbearing potential* must have a negative serum pregnancy test at screening and a negative urine pregnancy test within 24 hours prior to each study product injection

*Not sterilized via bilateral tubal ligation, bilateral oophorectomy, or hysterectomy, or, if menopausal, still menstruating or < 1 year of the last menses.

6. Women of childbearing potential must have used an acceptable form of contraception* in the 30 days prior to their first study product injection

*Acceptable single forms of contraception include abstinence from sexual activity that could lead to pregnancy, monogamous relationship with vasectomized partner who has been vasectomized for six months or more prior to enrollment, successful Essure® placement (permanent, non-surgical, non-hormonal sterilization), intrauterine devices, and hormonal methods, including the birth control patch, shot (Depo-Provera), pills, the vaginal ring (NuvaRing), and the contraceptive implant (Nexplanon). Acceptable barrier methods include diaphragm or cervical cap with spermicide and the contraceptive sponge.

7. Women of childbearing potential must agree to continue use of an acceptable form of contraception through 30 days after their last study product injection

8. Weight ≥ 50 kg and body mass index (BMI) < 35.0 kg/m²

9. Vital signs (oral temperature, pulse, and blood pressure) are within normal protocol-defined ranges*

*The normal protocol-defined ranges for vital signs include (a) oral temperature less than 38°C (100.4°F), (b) pulse no greater than 100 bpm, (c) systolic blood pressure 85 to 150 mmHg, inclusive, and (d) diastolic BP ≤ 100 mmHg.

10. Screening clinical lab values are all within normal protocol-defined reference ranges*

*The normal protocol-defined ranges for laboratory tests include (a) ALT of < 47 IU/L, (b) creatinine less than or equal to the laboratory upper limit of normal, (c) WBC $\geq 3.80 \times 10^3$ /UL and $\leq 13.00 \times 10^3$ /UL, (d) hemoglobin 11.5 g/dL or greater for females or 12.6 g/dL or greater for males, (e) platelets between 131×10^3 /UL and 415×10^3 /UL, inclusive.

Subject Exclusion Criteria

Subjects must not meet any of the exclusion criteria at baseline to be eligible for enrollment in this study.

1. Has had known schistosomiasis infection or has traveled to an endemic area for schistosomiasis infection and, during that travel, was potentially exposed to a *Schistosoma* species
2. Has been treated for schistosomiasis
3. Has previous exposure to schistosome vaccines or experimental products containing GLA-SE
4. Female subjects who are breastfeeding a child, or who plan to breastfeed a child from the first study product injection through 30 days after the last study product injection
5. Asthma, other than mild, well-controlled asthma*

*Cold or exercise-induced asthma controlled with inhaled medications other than inhaled corticosteroids is permissible. Subjects should be excluded if they require daily bronchodilator use or have had an asthma exacerbation requiring oral/parental steroid use or have used theophylline or inhaled corticosteroids in the past year.

6. Known atherosclerotic cardiovascular disease or history of myocardial infarction, pericarditis, or myocarditis
7. Diabetes mellitus
8. History of psychiatric condition that may make study compliance difficult, such as schizophrenia, or poorly controlled bipolar disorder*

*Includes persons with psychoses or history of suicide attempt or gesture in the 3 years before study entry or an ongoing risk for suicide.

9. Chronic or active neurologic condition (including seizures* and migraine headaches**)

*Seizure within the past 5 years.

**Four or more migraine headaches in the past 12 months that interfered with normal daily activity or any migraine headache in the past 5 years that required emergency or inpatient medical care.

10. Autoimmune disease*

*Autoimmune hypothyroidism with or without replacement therapy, and vitiligo or mild eczema or psoriasis not requiring chronic therapy, are permissible

11. Known or suspected congenital or acquired immunodeficiency including anatomic or functional asplenia* or immunosuppression as a result of underlying illness or treatment

*Any splenectomy is exclusionary

12. Use of alcohol or drugs that, in the opinion of the investigator, may interfere with ability to comply with the protocol or increase risk to subject's health during the study period

*Subjects with a history of malignancy may be included if treated by surgical excision, or by chemotherapy or radiation therapy and has been observed for a period that in the investigator's estimation provides a reasonable assurance of sustained cure (not less than 36 months).

Cervical neoplasia under surveillance and non-melanoma skin cancer are not exclusionary.

13. Active neoplastic disease*

*Subjects with a history of malignancy may be included if treated by surgical excision, or by chemotherapy or radiation therapy and has been observed for a period that in the investigator's estimation provides a reasonable assurance of sustained cure (not less than 36 months). Cervical neoplasia under surveillance and non-melanoma skin cancer are not exclusionary.

14. Chronic topical or systemic corticosteroid use*

*Corticosteroid nasal sprays for allergic rhinitis are permissible. Persons using a topical corticosteroid for a limited duration for mild uncomplicated dermatitis such as poison ivy or contact dermatitis prior to enrollment may be enrolled the day after their therapy is completed. Oral or parenteral (intravenous, IM, subcutaneous) corticosteroids given for non-chronic conditions not expected to recur are permissible if, within the year prior to enrollment, the longest course of therapy was no more than 14 days and no oral or parenteral corticosteroids were given within 30 days prior to enrollment. Intraarticular, bursal, tendon, or epidural injections of corticosteroids are permissible if the most recent injection was at least 30 days prior to enrollment. Topical or systemic corticosteroid use for study related AEs is not exclusionary.

15. Known contraindication to repeated phlebotomy*

*Such as minimal venous access or recent history of anemia

16. Receipt or planned receipt of inactivated vaccine or allergy desensitization injection within 14 days before or after a study product injection

17. Receipt or planned receipt of live attenuated vaccine 28 days before or after a study product injection

18. Receipt of blood products or immunoglobulin within six months prior to, or donation of unit of blood within two months prior to, the first study product injection.

19. Receipt of any experimental agent* within 30 days prior to screening or planned receipt prior to the last study visit**

*Vaccine, drug, biologic, device, blood product, or medication.

**Receipt of experimental COVID-19 related products are not necessarily exclusionary and will be evaluated on a case-by-case basis.

20. Plan to undergo surgery (elective or otherwise) within six months after study enrollment

21. Plans to enroll in another interventional clinical trial* at any time during the study period

*Includes trials evaluating interventions such as a drug, biologic, or device.

22. Positive confirmatory test for HIV infection

23. Positive serologic test for hepatitis B surface antigen (HBsAg)

24. Positive confirmatory test for hepatitis C virus (HCV) infection

25. Acute febrile illness (oral temperature $\geq 38^{\circ}\text{C}$) or other acute illness within three days prior to study product injection*

*Note for afebrile, acute illness only: If a subject is afebrile, his/her acute illness is nearly resolved with only minor residual symptoms remaining, and, in the opinion of the site PI or appropriate sub-investigator, the residual symptoms will not interfere with the ability to assess

safety parameters as required by the protocol, the subject may receive study product injection without further approval from the DMID Medical Officer.

26. Not willing to avoid donating blood during the study
27. Has any condition that would, in the opinion of the site investigator, place the subject at an unacceptable risk of injury or render the subject unable to meet the requirements of the protocol

4.4. Treatments

4.4.1. Treatments Administered

Each dose of study vaccine will be administered as a single 0.5-mL IM injection in the deltoid muscle of the participant's arm. Participants will be observed in the clinic for a minimum of 30 minutes following the study product injection. After 30 minutes, the injection site will be examined and the participant will be questioned about the presence of any localized or generalized reactogenicity symptoms. Any spontaneous AEs that occur will be assessed.

See the protocol-specific MOP for detailed information on the administration of the study product for each group. Treatment for each study group is summarized in [Table 1](#).

4.4.2. Identity of Investigational Product(s)

The vaccine product is a two-component system comprised of Sm-p80 antigen and GLA-SE adjuvant.

Sm-p80 for injection

Sm-p80 is a recombinant protein produced in *E. coli* bacteria. The protein antigen is the large subunit of the *S. mansoni* calcium-activated neutral protease, calpain. The Sm-p80 protein is formulated and lyophilized to yield the vaccine antigen, Sm-p80 for Injection. The final 758 amino acid protein antigen has a predicted mass of approximately 87kDa.

GLA-SE Adjuvant

GLA-SE is a synthetic Monophosphoryl Lipid A-like molecule which is a Toll-like receptor 4 agonist formulated in a SE to produce GLA-SE.

Sm-p80 + GLA-SE

Sm-p80 + GLA-SE contains the antigen and adjuvant. After reconstitution of the antigen with water-for-injection (WFI) and mixing with the liquid adjuvant, it is ready for administration to the study participant.

4.4.3. Method of Assigning Subjects to Treatment Groups (Randomization)

This is a non-randomized trial. Approximately 9 subjects will be assigned to each treatment arm.

4.4.4. Selection of Doses in the Study

Subjects receive 100 µg Sm-p80 alone or 10 µg, 30 µg, or 100 µg Sm-p80 with 5 µg GLA-SE.

The adjuvant dose of 5 µg of GLA-SE is selected for this trial as this dose is in the mid-range of doses evaluated in the 1100 previous subjects, has been shown to increase antibody levels and cellular immune responses, and has been evaluated in multiple clinical trials, including administering three vaccinations, demonstrating an acceptable safety profile. The preclinical studies of SchistoShield® do not inform the

selection of antigen dose for this study, as non-human primates require much higher doses of antigen and adjuvant than humans due to the tolerizing effects of their environment. In other vaccine trials in humans, GLA-SE adjuvant administered with antigen doses suggest that lower antigen doses are best to elicit T cell responses while the higher doses tend to elicit better humoral responses. Since it appears that the primary mechanism of action of SchistoShield® is mediated by humoral responses, this study will evaluate a range of Sm-p80 doses from 10 to 100 µg.

4.4.5. Selection and Timing of Dose for Each Subject

Subjects were evenly distributed between treatment arms. Each subject receives three doses of the study product on Days 1, 29, and 57 or Days 1, 29, and 180. Each dose of study vaccine will be administered as a single 0.5-mL IM injection in the deltoid muscle of the participant's arm. Detailed descriptions of study agent preparation and administration are found in the study MOP.

4.4.6. Blinding

This is an open-label clinical trial.

Subjects, investigators, study personnel performing any study-related assessments following study vaccine administration are not blinded to study treatment. Laboratory personnel performing immunologic assays will receive samples blinded to subject ID number and sample visit number.

4.4.7. Prior and Concomitant Therapy

Administration of any medications, therapies, or vaccines will be recorded on the appropriate eCRF. Concomitant medications will include all current medications and medications taken in the 60 days prior to the first vaccination and those taken from the time of vaccination through approximately 28 days after each vaccination, as described in Section 3.1. Medications reported in the electronic case report form (eCRF) are limited to those taken within 30 days prior to the first study product injection and those taken in the 28-day post-vaccination interval. Prescription and over-the-counter drugs will be included as well as herbals, vitamins, and supplements. In addition, receipt of non-study vaccines will be solicited from the time of each vaccination through approximately 28 days after each vaccination and reported in the eCRF. Use of a new medication should prompt evaluation for the occurrence of any MAAE, including a NOCMC.

Medications that might interfere with the evaluation of the investigational product(s) should not be used during the trial-reporting period (approximately 12 months after the last study vaccination) unless clinically indicated as part of the subject's health care. Medications in this category include the prohibited medications per the Subject Exclusion Criteria (see Section 4.3). In addition, the site PI or appropriate sub-investigator may identify other medications that should not be used due to a risk to subject safety or assessment of reactogenicity and immunogenicity.

4.4.8. Treatment Compliance

All subjects receive a total of three doses of study product delivered intramuscularly in the clinic by a qualified study personnel member according to subject treatment assignment.

4.5. Efficacy (Immunogenicity) and Safety Variables

As this is a Phase 1 clinical trial in healthy adult subjects, there is no assessment of drug efficacy. For a detailed schedule of activities, refer to [Table 2](#) and [Table 3](#). Refer to Section 3 for a list of primary and secondary objectives.

In general, multiple observations within a specific visit period will be accepted. In case of multiple observations within a specific window, the assessment value that is closest to the scheduled visit window will be used in the analyses for the post-baseline records. If observations have the same distance to the scheduled assessment, the latest one will be used. All recorded data will be listed.

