## 7.2      **Laboratory Evaluations**

### 7.2.1      **Clinical Laboratory Evaluations**

Subjects will be screened for HIV-1 and HIV-2 infection by a fourth-generation testing algorithm, for HCV infection, and for HBsAg. Screening labs also include WBC, hemoglobin, platelets, creatinine, and ALT.

Serum (screening visit) and urine (study product injection visits) pregnancy tests will be performed. Serum pregnancy tests will be performed by the Quest clinical diagnostic laboratory. Urine pregnancy CLIA-waved tests will be performed by research staff at the research site specimen processing laboratory. Pregnancy testing will be done at the screening visit and within 24 hours prior to each study product injection on all women of childbearing potential. Results must be negative and known prior to enrollment on Day 1 and administration of each study product injection.

Clinical safety laboratory parameters (WBC, hemoglobin, platelets, ALT, and creatinine) will be collected from each subject on the day of and prior to each study product injection, approximately 7 days after each study product injection, and approximately 28 days after each study product injection (which may also serve as the clinical safety laboratory samples for the second and/or third study product injection). These evaluations will be performed by the Quest laboratory. Venous blood samples will be collected for these safety labs. The results from the clinical safety laboratory parameters collected on the day of study product injections will not be available or reviewed prior to study product injection.

Laboratory values that are outside the range of eligibility but are thought to be due to an acute condition or due to laboratory error may be repeated once. One or more of the laboratory parameters may be repeated at any time during the study as determined by the PI, if indicated by an AE. A clinically significant abnormal value should be repeated within 10 days if possible and followed up as clinically relevant.

The volume of venous blood to be collected for the clinical safety laboratory evaluations is presented in Table 8 and Table 9.

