### **8.6.2 Individual Halting Criteria**

The study product injections will be discontinued in an individual if:

- The subject has a systemic hypersensitivity reaction following a study product injection that is judged related to the study product
- The subject has ulceration, abscess, or necrosis at the injection site related to study product administration.
- Presence of signs or symptoms that could confound or confuse assessment of study vaccine reactogenicity. For subjects with injection site or systemic signs or symptoms, or with an acute illness, including an oral temperature greater than or equal to 37.8°C, on the day of a scheduled study product injection, the study product injection should be postponed/deferred until the signs, symptoms, or acute illness have resolved, or are improving as further specified below, and if within the acceptable protocol-specified window for that visit No exceptions to the protocol-specified window will be made.

**Note for afebrile, acute illness only:** If a subject is afebrile, has an acute illness that is nearly resolved with only minor residual symptoms remaining, is still within the acceptable protocol-specified window for the study product injection and, in the opinion of the site PI or appropriate sub-investigator, the residual symptoms will not interfere with the ability to assess safety parameters as required by the protocol, the subject may receive the study product injection without further approval from the DMID Medical Officer. No exceptions to the protocol-specified window will be made.

- Any clinically significant medical condition that, in the opinion of the participating site PI or appropriate sub-investigator, poses an additional risk to the subject if they continue to participate in the study.
- Grade 3 clinical safety laboratory value (according to the Toxicity Tables [Appendix C](#)) that does not decrease to Grade 2 or less prior to the subsequent study product injection. Any clinical safety laboratory parameter may be re-evaluated only once prior to the subsequent study product injection. If the clinical safety laboratory value decreases to Grade 2 or less, the subject may receive the subsequent study product injection. The subsequent study

---

product injection should be scheduled to occur within the acceptable protocol-specific window for that visit. No exceptions to the protocol-specified window will be made.

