**Table 8: Schedule of Events and Study Procedures, Study Groups A, B, D, and E**

		Study Product Injection and Follow Up Visits												
Study day		1	2	4	8	29	32	36	57	60	64	85	181	422
Days after most recent vaccination		0	1	3	7	28	3	7	28	3	7	28	124	365
Visit Window (± number of days)		0	0	1	1	3	1	1	3	1	1	3	14	14
Study visit		01	02P	03	04	05	06	07	08	09	10	11	12	13P
Clinical Evaluations and Procedures	Tube													
Assessment of eligibility		X												
Assessment of individual halting criteria						X			X					
Review medical history and con meds 		X	X	X	X	X	X	X	X	X	X	X	X	X
Vital signs (blood pressure, pulse, and oral temperature  )		X		X	X	X	X	X	X	X	X	X 	X 	
Enrollment		X												
Study Product Injection		I-1				I-2			I-3					
Targeted physical exam		{X}		{X}	{X}	{X}	{X}	{X}	{X}	{X}	{X}	{X}	{X}	
Pre-administration reactogenicity assessment		X				X			X					
Evaluate study product injection site		X		X	X	X	X	X	X	X	X			
Provide and explain use of memory aid and thermometer		X				X			X					
Review memory aid			X	X	X		X	X		X	X			
Collection of solicited AEs		X	X	X	X	X	X	X	X	X	X			

		Study Product Injection and Follow Up Visits												
Study day		1	2	4	8	29	32	36	57	60	64	85	181	422
Days after most recent vaccination		0	1	3	7	28	3	7	28	3	7	28	124	365
Visit Window ( $\pm$ number of days)		0	0	1	1	3	1	1	3	1	1	3	14	14
Study visit		01	02P	03	04	05	06	07	08	09	10	11	12	13P
Clinical Evaluations and Procedures	Tube													
Collection of unsolicited AEs and SAEs 		X	X	X	X	X	X	X	X	X	X	X	X	X
Pregnancy test (urine) 		X				X			X					
WBC, hemoglobin, platelets (mL)	EDTA	3			3	3		3	3		3	3		
Creatinine, ALT 	SST	10			10	10		10	10		10	10		
Serum collection for antibody assays and secondary research (mL)	SST	8.5			8.5	8.5		8.5	8.5		8.5	8.5	8.5	
PBMC isolation for secondary research (mL)	NaHep/ACD 	60			60	60		60	60		60	34	60	
Whole blood collection for gene expression assays	PAXGene	2.5			2.5	2.5		2.5	2.5		2.5			
Total volume per visit (mL)		84			84	84		84	84		84	55.5	68.5	
Cumulative volume (prior 56 days)		113.5			197.5	281.5		365.5	420		420	391.5	68.5	

{ } required at this visit only if clinically indicated

P=phone assessment

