14.3.5 Displays of Laboratory Results

14.3.5.1 Chemistry Results

Table 59: Laboratory Results by Parameter, Maximum Severity, Time Point, and Treatment Group – Any Chemistry Parameter

[Implementation Note: Add group name to treatment, e.g. "Group A: 100 µg Sm-p80 (unadjuvanted)".]

Time Point	Treatment Group	N	None		Mild / Grade 1		Moderate/ Grade 2		Severe/ Grade 3		Missing	
			n	%	n	%	n	%	n	%	n	%
Study Day 1 (Baseline)	100 µg Sm-p80 (unadjuvanted)	x	x	xx	x	xx	x	xx	x	xx	x	xx
	10 µg Sm-p80 + 5 µg GLA-SE											
	30 µg Sm-p80 + 5 µg GLA-SE (delayed booster)											
	30 µg Sm-p80 + 5 µg GLA-SE											
	100 µg Sm-p80 + 5 µg GLA-SE											
Study Day 8	100 µg Sm-p80 (unadjuvanted)											
	10 µg Sm-p80 + 5 µg GLA-SE											
	30 µg Sm-p80 + 5 µg GLA-SE (delayed booster)											
	30 µg Sm-p80 + 5 µg GLA-SE											
	100 µg Sm-p80 + 5 µg GLA-SE											
Study Day 29	100 µg Sm-p80 (unadjuvanted)											
	10 µg Sm-p80 + 5 µg GLA-SE											
	30 µg Sm-p80 + 5 µg GLA-SE (delayed booster)											
	30 µg Sm-p80 + 5 µg GLA-SE											
	100 µg Sm-p80 + 5 µg GLA-SE											
Study Day 36	100 µg Sm-p80 (unadjuvanted)											

**Table 59: Laboratory Results by Parameter, Maximum Severity, Time Point, and Treatment Group – Any Chemistry Parameter
(Continued)**

Time Point	Treatment Group	N	None		Mild / Grade 1		Moderate/ Grade 2		Severe/ Grade 3		Missing	
			n	%	n	%	n	%	n	%	n	%
	10 µg Sm-p80 + 5 µg GLA-SE											
	30 µg Sm-p80 + 5 µg GLA-SE (delayed booster)											
	30 µg Sm-p80 + 5 µg GLA-SE											
	100 µg Sm-p80 + 5 µg GLA-SE											
Study Day 57	100 µg Sm-p80 (unadjuvanted)											
	10 µg Sm-p80 + 5 µg GLA-SE											
	30 µg Sm-p80 + 5 µg GLA-SE (delayed booster)											
	30 µg Sm-p80 + 5 µg GLA-SE											
	100 µg Sm-p80 + 5 µg GLA-SE											
Study Day 64	100 µg Sm-p80 (unadjuvanted)											
	10 µg Sm-p80 + 5 µg GLA-SE											
	30 µg Sm-p80 + 5 µg GLA-SE											
	100 µg Sm-p80 + 5 µg GLA-SE											
Study Day 85	100 µg Sm-p80 (unadjuvanted)											
	10 µg Sm-p80 + 5 µg GLA-SE											
	30 µg Sm-p80 + 5 µg GLA-SE											
	100 µg Sm-p80 + 5 µg GLA-SE											
Study Day 180	30 µg Sm-p80 + 5 µg GLA-SE (delayed booster)											
Study Day 187	30 µg Sm-p80 + 5 µg GLA-SE (delayed booster)											

Table 59: Laboratory Results by Parameter, Maximum Severity, Time Point, and Treatment Group – Any Chemistry Parameter (Continued)

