Table 62: Abnormal Laboratory Results Related to Study Treatment by Parameter, Maximum Severity, Time Point, and Treatment Group – Any Chemistry Parameter (Continued)

Time Point	Treatment Group	N	None		Mild / Grade 1		Moderate/ Grade 2		Severe/ Grade 3	
			n	%	n	%	n	%	n	%
Study Day 57	100 µg Sm-p80 (unadjuvanted)									
	10 µg Sm-p80 + 5 µg GLA-SE									
	30 µg Sm-p80 + 5 µg GLA-SE (delayed booster)									
	30 µg Sm-p80 + 5 µg GLA-SE									
	100 µg Sm-p80 + 5 µg GLA-SE									
Study Day 64	100 µg Sm-p80 (unadjuvanted)									
	10 µg Sm-p80 + 5 µg GLA-SE									
	30 µg Sm-p80 + 5 µg GLA-SE									
	100 µg Sm-p80 + 5 µg GLA-SE									
Study Day 85	100 µg Sm-p80 (unadjuvanted)									
	10 µg Sm-p80 + 5 µg GLA-SE									
	30 µg Sm-p80 + 5 µg GLA-SE									
	100 µg Sm-p80 + 5 µg GLA-SE									
Study Day 180	30 µg Sm-p80 + 5 µg GLA-SE (delayed booster)									
Study Day 187	30 µg Sm-p80 + 5 µg GLA-SE (delayed booster)									
Study Day 208	30 µg Sm-p80 + 5 µg GLA-SE (delayed booster)									
Max Severity Post Baseline	100 µg Sm-p80 (unadjuvanted)									
	10 µg Sm-p80 + 5 µg GLA-SE									
	30 µg Sm-p80 + 5 µg GLA-SE (delayed booster)									
	30 µg Sm-p80 + 5 µg GLA-SE									
	100 µg Sm-p80 + 5 µg GLA-SE									

Table 62: Abnormal Laboratory Results Related to Study Treatment by Parameter, Maximum Severity, Time Point, and Treatment Group – Any Chemistry Parameter (Continued)

Time Point	Treatment Group	N	None			Mild / Grade 1		Moderate/ Grade 2		Severe/ Grade 3			
			n	%	n	%	n	%	n	%	n		
Note: The “Max Post Baseline” rows indicate the maximum severity experienced by each subject at any time point post baseline.													
Note: N = Number of subjects in the Safety Population with lab results at the specified visit.													

Tables with similar format to [Table 62](#):

Table 63: Abnormal Laboratory Results Related to Study Treatment by Parameter, Maximum Severity, Time Point, and Treatment Group – Creatinine

Table 64: Abnormal Laboratory Results Related to Study Treatment by Parameter, Maximum Severity, Time Point, and Treatment Group – Alanine Aminotransferase

Table 65: Laboratory Summary Statistics by Parameter, Time Point, and Treatment Group – Creatinine (mg/dL)

[Implementation Note: Add group name to treatment, e.g. "Group A: 100 µg Sm-p80 (unadjuvanted)."]

Time Point	Treatment Group	N	Mean	Standard Deviation	Median	Min, Max
Study Day 1 (Baseline)	100 µg Sm-p80 (unadjuvanted)	x	xx.x	xx.x	xx.x	xx, xx

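### The one-value-per-window rule in SAP 4.5 lets a repeat draw replace an abnormal laboratory grade in the by-visit severity rows, so the per-dose display can be understated

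*SAP*

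**What the plan says.** SAP 4.5, which covers both immunogenicity and safety variables, reduces multiple observations in a window to one: "the assessment value that is closest to the scheduled visit window will be used in the analyses for the post-baseline records". Ties are settled by a second sentence: "If observations have the same distance to the scheduled assessment, the latest one will be used". The rule is introduced as a general one. It has no exception for graded laboratory results or for draws prompted by an abnormal value. The next sentence adds: "All recorded data will be listed".

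Protocol 7.2.1 expects such draws: "A clinically significant abnormal value should be repeated within 10 days if possible and followed up as clinically relevant". Protocol 8.6.2 adds: "Any clinical safety laboratory parameter may be re-evaluated only once prior to the subsequent study product injection". Protocol 6.3 and 7.2.1 say that laboratory results from the day of an injection are not reviewed before that injection.

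The tables concerned are by-visit displays of grade. Table 59, for example, is titled "Laboratory Results by Parameter, Maximum Severity, Time Point, and Treatment Group – Any Chemistry Parameter". SAP 9.6 assigns Tables 59-61 and 67-70 to severity by time point, and Tables 62-64 and 71-74 to results related to treatment. It does not say how a repeat in the same window is handled. Each table ends with a row for maximum severity after baseline. The notes to Tables 59, 67 and 71 say that this row includes unscheduled assessments. The Table 62 note, whose format also serves Tables 63-64, says only that its "rows indicate the maximum severity experienced by each subject at any time point post baseline".

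**The concern.** The selection rule depends on timing, but the reason for a second draw is often the first result. A repeat taken because a value was abnormal will tend to be milder, through recovery or regression to the mean. If it is nearer the scheduled day, or tied, it becomes the value for that visit. A row in a table titled as maximum severity would then show something other than the maximum.

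Injection visits add a second problem. The draw is taken before the dose and its result is not yet known. If the dose is given, a repeat on a later day is a post-dose sample. SAP 4.5.1 lets the 28-day sample double as the pre-dose sample for the next injection. The rule can therefore put a value from after dose 2 into the Day 29 row, which is the 28-days-after-dose-1 row.

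The laboratory endpoint in SAP 3.2.1 is primary and runs from each vaccination to about 28 days after it. The maximum row pools all doses, so aggregate information per dose comes from the by-visit rows. Tables 59-61 and 67-70 are also in the interim package (SAP 6.2), and SAP 6.6.2 allows interim results to be presented publicly. With nine subjects per group, one changed grade moves a cell by 1/9, about 11 percentage points.

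**Working it through.** The documents give no figure for this rule, so there is none to reproduce. The check enumerates what the rule does.

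**Inputs**
- Windows at post-baseline laboratory visits (Protocol Tables 8 and 9): ±1 day at Days 8, 36, 64 and 187; ±3 days at Days 29, 57, 85 and 208; ±7 days at Day 180 (Group C).
- Repeat delay: Protocol 7.2.1 says within 10 days if possible. Delays of 1-3 days and of 1-10 days are both shown, as assumptions.
- Reference point: the first sentence of the rule refers to the window and the tie sentence to the scheduled assessment. The scheduled day is used here.

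**Formula.** Let v be the first draw's offset from the scheduled day and d the delay to the repeat. The repeat displaces the first value when it is in the window and |v + d| ≤ |v|, with equality counting because ties go to the latest.

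**±3-day visits, d = 1 to 3** (7 × 3 = 21 pairs)
- v = -3: repeat at -2, -1 or 0; all 3 displace.
- v = -2: repeat at -1, 0 or 1; all 3 displace.
- v = -1: repeat at 0 or 1 displaces, at 2 does not; 2 displace.
- v = 0 to 3: none.
- Total: 3 + 3 + 2 = 8 of 21 (38%).

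**d = 1 to 10**

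| Window | Pairs | Displacing pairs |
|---|---|---|
| ±1 day | 30 | 2 (7%) |
| ±3 days | 70 | 6 + 4 + 2 = 12 (17%) |
| ±7 days | 150 | 50 (33%) |

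These are counts of possible day-pairs, given that a repeat is taken. They are not probabilities. Displacement by a repeat on a later day needs a first draw before the scheduled day.

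**Illustration.** ALT is 180 IU/L on Day 28, drawn before dose 2 that day. This is Grade 3 in SAP Table 7 (above 175). A repeat on Day 30 gives 60 IU/L, Grade 1 (47-105). Both are one day from Day 29, so the later is used. The Day 29 row shows Grade 1, from a sample taken two days after dose 2.

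**What is kept.** The Grade 3 value remains in the maximum row of Tables 59 and 61, in the abnormal-result listing (Table 57) and in Listing 13. The subject-level loss from the maximum rows of Tables 59-61 and 67-70 is zero.

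**The case against.** The strongest reply is that nothing is lost. SAP 4.5 lists all recorded data, Tables 57-58 list every abnormal result with its grade, relationship and actual study day, and the maximum rows keep the worst grade. That is right, and a reader who inferred that graded abnormalities vanish from the report would be wrong. It does not restore the per-dose aggregate view, because the maximum row has no dose dimension.

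A second reply is that a prompted repeat is an unscheduled draw (Protocol 6.4 gives it a supplemental form) and so never competes for a scheduled-visit row. The table notes mention unscheduled assessments only for the maximum row. This may be what the authors intend, but SAP 4.5 speaks of observations in a window without that distinction and SAP 9.6 is silent. A programmer following the text as written would apply the rule.

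Three stronger inferences should not be drawn:
- That the latest in-window value always wins, because every such value is at distance zero from the window. This would give 15 of 21 pairs (71%). The tie sentence points to the scheduled assessment, and on the other reading the word closest would do no work.
- That the shift is always towards a lower grade. A repeat can be worse, and some repeats follow an adverse event or a hemolysed or clotted sample rather than an abnormal value.
- That the Table 62 note drops unscheduled draws. Its reference to any post-baseline time point already covers them; the difference from the other notes is inconsistent wording.

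The re-evaluation clause in Protocol 8.6.2 adds little. It can be used at any time before the next injection, which for a Day 8 value is mostly outside the ±1-day window.

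**Conclusion.** The point holds as a small, correctable fault in a stated rule. As written, SAP 4.5 can fill a by-visit severity cell in Tables 59-64 and 67-74 with a repeat in place of the abnormal value that prompted it. At injection visits it can credit a post-dose sample to the previous dose. The likely direction is understatement of the per-dose aggregate display of a primary safety endpoint.

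The size depends on how often repeats are taken, which the documents do not give, so the number of affected cells cannot be estimated. Given a repeat, and measuring distance to the scheduled day, the share of displacing day-pairs at ±3-day visits is 8 of 21 for delays of 1-3 days and 12 of 70 for 1-10 days. It is much lower at ±1-day visits. Subject-level maximum severity and the listings are intact, and nothing here shows an effect on the halting rules.

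**What to change.** In SAP 4.5:
- Limit the one-value rule to continuous and immunogenicity summaries. Use the scheduled sample (the pre-dose sample on injection days), and one reference point, the scheduled day.
- For graded by-visit laboratory rows (Tables 59-64 and 67-74), use the worst grade in the visit window and before the next dose. A repeat drawn after that dose then stays in the listings and the maximum row and is not credited to the earlier dose.

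In SAP Appendix 1, add the words on unscheduled assessments to the Table 62 note, to match Tables 59, 67 and 71.

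With these changes, displacement of an abnormal value by a milder repeat is zero under either reading of distance, and the maximum rows of Tables 59-61 and 67-70 do not change. The cost is a few sentences and a little programming. By-visit severity may look slightly less favourable.
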